**4. What is your plan for primary variable analysis?**

One-sided test for proportions

**5. What is your plan for secondary variable analysis?**

N/A. We are only conducting a primary analysis.

**6. Have you been working with a statistician in designing this protocol? Yes**

IF YES, what is their name? [name]

Will data from multiple sites be combined during analysis? Yes

### Information from Outside Institution

**INSTRUCTIONS:**

You will need to submit an IRB approval or documentation from the outside institution documenting that they approve of this study being done at their site and info being shared with UVa.

In order to obtain information from other sites in the future, you will be required to submit a modification of this protocol to the IRB-HSR.

**2. Describe the type of information you will receive from each site.**

Answer/Response: We will receive de-identified subject demographics, infection information, pertinent dates, surgical procedures performed, and information re: treatment

**3. Does the outside institution have an IRB?**

Answer/Response: Yes.

IF NO, list the names of the individuals who will be supplying the data and/or specimens.

**INSTRUCTIONS:** You will be required to submit a signed Unaffiliated Investigator Agreement for each person listed.

Answer/Response:

### Biomedical Research

**1. What will be done in this protocol?**

Patients who present with open fractures to UVA Health System will be approached for participation in the study. After obtaining Informed consent, subjects will be randomized to Antibiotic Arm (experimental) or Placebo. Administration of the local antibiotic in this study is being done solely for answering a research question on the efficacy of the antibiotic tobramycin in decreasing the risk and rate of infection.

Subjects will be randomized to the experimental group, who will be injected locally at the wound cavity (i.e. fracture site, surrounding soft tissue which include muscle, and subcutaneous space) with 80mg/40mL of tobramycin after wound closure, and placebo group who will be injected locally with 40 mL 0.9% NS after wound closure. Systemic antibiotic will not be withheld and will be done along side the local injection of tobramycin. If patient returns to the OR for repeat debridement procedures, the injection will be repeated. If patient returns to the OR for repeat debridement procedures, the injection will be repeated. The second injection will only be given if the subject undergoes a repeat procedure, and will be given two days later than the first injection. By this time, serum tobramycin levels would have normalized, given the low doses and time interval. . Dose volume will not be adjusted because the safety of this antibiotic assumes that the patient weighs at least 16 kg, and any patient 18 years or older will weigh more than that. While systemic antibiotic treatment is standard of care, animal studies and early clinical case series data indicated that injection of aqueous aminoglycoside after wound closure locally could be a highly effective technique for wound infection prophylaxis[1]. In this study protocol, other aminoglycosides (eg. Gentamycin) will be allowed as part of standard systemic prophylaxis.

Follow up data will be collected at 2 weeks, 6 weeks. Clinical data will be collected from medical records

**2. List the procedures, in bullet form, that will be done for RESEARCH PURPOSES as stipulated in this protocol.**

- Medical record review at baseline and all subsequent study weeks up to 1 year after surgery
- Randomization to Antibiotic ( tobramycin) arm or Placebo before surgery by clinical pharmacy program at UVA.
- Experimental group will have the close wound injected with 80 mg/40mL of tobramycin at the END of surgery
- Control group will have 40 mL 0.9%NS injected into the closed wound at the end of the case
- Follow up at 2 and 6 weeks at the clinic. *These visits to the clinic will coincide with the follow up as in standard of care for open fracture management.*

**3. Will you be using data/specimens in this study that were collected previously, with the use of a research consent form, from another research study? NO**

**4. Will any of the procedures listed in item # 2 have the potential to identify an incidental finding? This includes ALL procedures, assessments and evaluations that are being done for RESEARCH PURPOSES that may or may not be considered investigational. yes**

► IF YES, check one of the following two options:

The examination(s) utilize(s) the same techniques, equipment, etc., that would be used if the subject were to have the examination(s) performed for clinical care. **There exists the potential for the discovery of clinically significant incidental findings.**

- The PI takes full responsibility for the identification of incidental findings:
- The PI will inform the subjects verbally of all incidental findings that are of clinical significance or are of questionable significance.
- A follow-up letter describing the finding should be provided to the subject with instructions to either show the letter to their PC or if the subject has no PCP, the subject should be instructed to make an appointment at UVa or at the Free Clinic.

**5. Do any of the procedures listed above, under question # 2, utilize any imaging procedures for RESEARCH PURPOSES? No**

**6. Will you be using viable embryos? NO**

**Will you be using embryonic stem cells? NO**

**7. Are any aspects of the study kept secret from the participants? NO**

**Is any deception used in the study? NO**

If this protocol involves study treatment, explain how a subject will be transitioned from study treatment when they have completed their participation in the study. **NA**

**2. Will any data/specimens be sent to UVa for analysis from the sites outside of UVa?**

Only data. There will be no data sent from UVA to other sites, data will only flow TO UVA.

► **IF YES, do you confirm you will have received a copy of the IRB approval from the outside site before receiving data/specimens from them?** Yes, confirmed.

**3. Do you confirm you will have a Material Transfer Agreement (MTA) through the Grants and Contracts office prior to sending or receiving data/specimens?** Yes, confirmed

**4. Describe the process for sharing safety concerns.** We will have conference calls no less than twice per year. If a SAE occurs and if it is deemed unexpected AND related there will be a conference call within 5 days with the site-PI's.

### INSTRUCTIONS

- e.g. weekly conference calls, use of SAE forms, overall safety monitor etc.

- include frequency of communication
- identify participants ( by role) in this process

Collaborative Site Analysis Studies DSMP			
Type of Event	To whom will it be reported:	Time Frame for Reporting	How reported?
*Serious, unexpected and related or possibly related adverse events	All Research Sites	Within 15 days after the site PI receives knowledge of the event.	IND/IDE Safety Report (Cover letter, copy of MedWatch/narrative)
*Unanticipated Problem	All Research Sites	Within 15 calendar days from the time the Site PI receives knowledge of the event.	Letter to Participating PIs, Copy of MedWatch or narrative
Protocol Violations/Noncompliance The IRB-HSR only requires that MAJOR violations be reported, unless otherwise required by the sponsor.	All Research Sites	Within 7 calendar days from the time the study team received knowledge of the event.	Protocol Violation, Noncompliance and Enrollment Exception Reporting Form http://www.virginia.edu/vprgs/irb/hsr_forms.html Go to 3 rd bullet from the bottom.

\*as defined in each sites protocol

## Data and Safety Monitoring Plan.

### 1. Definition:

#### 1.1 How will you define adverse events (AE) for this study?

An adverse event will be considered any undesirable sign, symptom or medical or psychological condition **even if the event is not considered to be related** to the investigational drug/device/intervention. Medical condition/diseases present before starting the investigational drug/intervention will be considered adverse events only if they worsen after starting study treatment/intervention. An adverse event is also any undesirable and unintended effect of research occurring in human subjects as a result of the collection of identifiable private information under the research. Adverse events also include any problems associated with the use of an investigational device that adversely affects the rights, safety or welfare of subject s.

#### 1.2 How will you define serious adverse events?

A serious adverse event will be considered any undesirable sign, symptom, or medical condition which is fatal, is life-threatening, requires or prolongs inpatient hospitalization, results in persistent or significant disability/incapacity, constitutes a congenital anomaly or birth

defect, is medically significant and which the investigator regards as serious based on appropriate medical judgment. An important medical event is any AE that may not result in death, be life-threatening, or require hospitalization but may be considered an SAE when, based upon appropriate medical judgment, it may jeopardize the patient and may require medical or surgical intervention to prevent one of the outcomes listed in the definitions of SAEs.

### **1.3 What is the definition of an unanticipated problem?**

Do not change this answer

An unanticipated problem is any event, experience that meets ALL 3 criteria below:

- Is unexpected in terms of nature, severity or frequency given the research procedures that are described in the protocol-related documents AND in the characteristics of the subject population being studied
- Related or possibly related to participation in research. This means that there is a reasonable possibility that the incident may have been caused by the procedures involved in the research study.
- The incident suggests that the research placed the subject or others at greater risk of harm than was previously known or recognized OR results in actual harm to the subject or others

### **1.4 What are the definitions of a protocol violation and/or noncompliance?**

Do not change this answer

A **protocol violation** is defined as any change, deviation, or departure from the study design or procedures of research project that is NOT approved by the IRB-HSR prior to its initiation or implementation. Protocol violations may be major or minor violations.

**Noncompliance** can be a protocol violation OR deviation from standard operating procedures, Good Clinical Practices (GCPs), federal, state or local regulations. Noncompliance may be serious or continuing.

Additional Information: see the IRB-HSR website at

[http://www.virginia.edu/vpr/irb/HSR\\_docs/Forms/Protocol\\_Violations\\_%20Enrollment\\_Exceptions\\_Instructions.doc](http://www.virginia.edu/vpr/irb/HSR_docs/Forms/Protocol_Violations_%20Enrollment_Exceptions_Instructions.doc)

### **1.5 If pregnancy occurs how will this information be managed?**

X  Adverse Event- will follow adverse event recording and reporting procedures outlined in section 3.

### **1.6 What is the definition of a Protocol Enrollment Exception?**

X  NA- No outside sponsor

### **1.7 What is the definition of a data breach?**

Do not change this answer

A data breach is defined in the HITECH Act (43 USC 17932) as an unauthorized acquisition, access, or use of protected health information (PHI) that compromises the security or privacy of such information.

Additional Information may be found on the IRB-HSR Website: [Data Breach](#)

## 2. Identified risks and plans to minimize risk

### 2.1 What risks are expected due to the intervention in this protocol?

Expected Risks related to study participation.	Frequency
Nephrotoxicity	 Occurs frequently  Occurs infrequently  Occurs rarely  Frequency unknown
Neurotoxicity manifested by ototoxicity – vestibular and auditory	 Occurs frequently  Occurs infrequently  Occurs rarely  Frequency unknown
Neurotoxicity manifested by numbness, skin tingling, muscle twitching and convulsions (in patients with preexisting renal damage and normal renal function with prolonged exposure to tobramycin)	 Occurs frequently  Occurs infrequently  Occurs rarely  Frequency unknown
Nephrotoxicity in patients with impaired renal function and in those who received high dose of tobramycin for prolonged period	 Occurs frequently  Occurs infrequently  Occurs rarely  Frequency unknown
Violation of subject's privacy and confidentiality	Minimized due to the requirements of the privacy plan in this protocol

### 2.2 List by bullet format a summary of safety tests/procedures/observations to be performed that will minimize risks to participants:

- Renal and eighth cranial nerve function will be closely monitored, especially in patients with known or suspected reduced renal function at onset of therapy and also in those whose renal function is initially normal but who develop signs of renal dysfunction during therapy.
- Urine will be examined for decreased specific gravity, increased excretion of protein and the presence of cells or casts.

- Blood urea nitrogen (BUN), serum creatinine or creatinine clearance will be determined per standard of care during hospitalization.
- Evidence of ototoxicity (dizziness, vertigo, tinnitus, roaring in the ears or hearing loss) or cephrotoxicity will prompt closer monitoring and consultation of ENT and/or the nephrology teams.
- Concurrent and/or sequential systemic or topical use of other potentially neurotoxic and nephrotoxic drugs including: cisplatin, cephaloridine, kanamycin, amikacin, neomycin, polymyxin B, colistin, paromomycin, streptomycin, vancomycin, and viomycin will be avoided. Age and dehydration which increase the risk of toxicity will be monitored. Concurrent use of tobramycin with potent diuretics such as ethacrynic acid or furosemide will be avoided. All patients on diuretics will have them held on the day prior to surgery to avoid complications. Diuretics will be withheld after subject signs Informed consent
- Injecting the drug directly into the fracture site will pose no greater than risk than intramuscular injection of tobramycin.

Clinical care team will be notified of the need to avoid other potentially nephrotoxic or neurogenic agents. A note will be put in Epic to this effect.

**2.3 Under what criteria would an INDIVIDUAL SUBJECT'S study treatment or study participation be stopped or modified**

Treatment would be stopped if the subject had a serious adverse event deemed related to study, or study drug will be increased if the subject tolerates dosing

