**2.4 Under what criteria would THE ENTIRE STUDY need to be stopped.**

Per IRB, PI, DSMB, or sponsor discretion

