**5.3. What items will be included in the aggregate review conducted by the PI?**

NA- PI is not the overall person overseeing the safety data for this study.  
 All adverse events  
 Unanticipated Problems  
 Protocol violations/Issues of noncompliance  
 Audit results  
 Application of dose finding escalation/de-escalation rules  
These should be outlined under 2.4.  
 Application of study designed stopping/decision rules  
 Early withdrawals  
 Whether the study accrual pattern warrants continuation/action  
 Endpoint data  
 Other: Specify Answer/Response:

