**3. What dose will be utilized in this study?**

Trobramycin 80mg/40mL

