**7. Will drug need to be prepared by the UVa Investigational Drug Service (IDS)?**

Investigational pharmacy will store the drug and perform the randomization to drug or placebo, and provide the drug to the surgeons on the day of surgery. The randomization code will be stored by the **IDS Pharmacy** on a spreadsheet.

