**8. Are there any special handling instructions mandated by the study (e.g. weighing hazardous materials)?**

No

**9. Does the protocol provide provisions for dose titration, dose reductions, and or re-challenged (if drug is stopped), etc.? No**

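### The individual-subject modification rule (DSMP 2.3) calls for a dose increase that contradicts the fixed 80 mg/40 mL injection; the clause should be deleted

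*Combined protocol and SAP*

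**What the plan says.** DSMP 2.3 sets out when one subject's treatment is stopped or modified. Its first half stops treatment after a related serious adverse event. Its second half says that "study drug will be increased if the subject tolerates dosing".

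The other dosing statements are:

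- Appendix: Pharmacy, item 9: "Does the protocol provide provisions for dose titration, dose reductions, and or re-challenged (if drug is stopped), etc.? No"
- Appendix: Pharmacy, item 3, the study dose: "Trobramycin 80mg/40mL"
- Biomedical Research, item 2: "Experimental group will have the close wound injected with 80 mg/40mL of tobramycin at the END of surgery". Statistical Considerations, item 2, gives the same 80 mg in 40 mL for the active arm.
- Biomedical Research, item 1: "Dose volume will not be adjusted", a statement justified there by body weight.
- Biomedical Research, item 1, also provides for another injection, two days after the first, if the subject goes back to the operating room for further debridement. Appendix: Pharmacy, item 4, gives the frequency as once and then says that a second dose follows the same randomized assignment.

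Two arguments elsewhere rest on one dose only. The Safety Summary sets aside the concern about renal impairment because a single 80 mg dose is given. Statistical Considerations, item 2, gives a single dose as the reason for having no early-stopping contingencies.

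**The concern.** Item 2.3 is an operative rule, and its wording is mandatory. Read literally, it tells staff to raise the dose of an aminoglycoside in anyone who tolerates it, while the pharmacy appendix says that no titration exists. Both cannot be right. At a repeat injection, keeping the dose would depart from 2.3 and raising it would depart from the pharmacy appendix, so either action conflicts with some part of the approved plan. If the clause were acted on, the active arm would also stop being one defined treatment.

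The single-dose wording is a smaller matter of the same kind. A safety argument and a monitoring decision each give a reason that is not true of a subject who is injected twice.

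**Working it through.** **1. The plan's own figures.** The inputs are in the Safety Summary.

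- Local concentration = dose / volume = 80 mg / 40 mL = 2 mg/mL. This matches the plan.
- Intravenous comparator = 5 mg/kg × 70 kg = 350 mg. This also matches.

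**2. The clause against the fixed dose.** Pharmacy item 9 rules out titration. Pharmacy item 3, Biomedical Research item 2 and Statistical Considerations item 2 each give 80 mg in 40 mL. Pharmacy item 4 makes any second injection the same assigned treatment. Item 9 carries the contradiction most directly. The statement on dose volume is weaker support, because its stated reason is body weight and not tolerance.

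**3. What an increase would do to the tissue-safety argument.** For a dose D in 40 mL, concentration = D/40, which exceeds 2 mg/mL whenever D is above 80 mg. Holding 2 mg/mL would need a volume of D/2 mL, which exceeds 40 mL whenever D is above 80 mg. So any increase departs either from the concentration on which the Safety Summary relies or from the stated volume. The size of the increase cannot be calculated, because 2.3 gives none.

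**4. Where the clause could apply.** The investigational pharmacy is to "provide the drug to the surgeons on the day of surgery", and the injection is given once the wound is closed. The only later dosing occasion is the injection at a repeat debridement. Statistical Considerations, item 1, keeps the surgeon blinded to the arm.

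**5. Cumulative dose with one repeat.**

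- Total = 2 × 80 = 160 mg.
- At 70 kg: 80/70 = 1.14 mg/kg for one injection; 160/70 = 2.29 mg/kg for two.
- Against the 350 mg comparator: 80/350 = 22.9%; 160/350 = 45.7%, counting no clearance between injections.

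These figures count study drug only. The plan also allows systemic aminoglycosides as standard prophylaxis.

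**6. Statistical quantities.** The sample size uses infection rates of 10% and 1%, one-sided alpha 0.05 and power 70%. The normal-approximation formula for two proportions, without continuity correction, returns the stated 60 per group. No dose enters it, so deleting the clause changes nothing there.

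**The case against.** The strongest reply is that this is leftover text. No escalation was designed, and a blinded surgeon working with pharmacy-supplied syringes could hardly carry one out. That stands, and it keeps the practical risk low. It does not make the sentence correct, and this is the item staff would consult on modifying a subject's treatment.

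A second reply is that the repeat injection is disclosed, and that Biomedical Research, item 1, gives its own rationale for it. That also stands. The single-dose point is therefore one of wording, and no decision depends on it.

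Four stronger readings are tempting, but the documents do not support them:

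- *Nothing in the safety case covers more than 80 mg.* The Safety Summary's systemic argument cites routine single intravenous doses of 4–7 mg/kg. Only the local-tissue argument is tied to the 80 mg/40 mL preparation.
- *An escalation rule is missing from 2.4.* DSMP 5.3 says "These should be outlined under 2.4", but that is template text beneath a form option whose checkbox state cannot be seen. Item 2.4 concerns stopping the whole study, so its silence on escalation shows nothing.
- *Injections are unlimited.* No maximum is written down, but both places that describe the repeat speak of a second injection or dose. They read most naturally as at most two.
- *Two days is too short in renal insufficiency.* Such subjects are eligible, but nothing in the documents shows the interval to be unsafe at this dose. DSMP 2.2 commits to close renal monitoring, especially where function is reduced. The Safety Summary has the primary team told of the intra-operative dose if systemic aminoglycosides continue.

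**Conclusion.** The dose-increase clause in DSMP 2.3 is wrong as written. It conflicts directly with the answer on titration and with a dose fixed at 80 mg/40 mL in the pharmacy, procedure and statistical sections. Any increase at 40 mL would exceed the 2 mg/mL behind the tissue-safety argument.

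The practical exposure risk is low, and this is a correction of text, not evidence of harm. That judgment assumes that the fixed dose is what the sponsor intends, as the dosing sections indicate, and that the repeat at debridement is the only later dosing occasion.

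The single-dose wording is a minor alignment: it is inaccurate for a re-injected subject, whose total after one repeat is 160 mg and not 80 mg. The share of subjects re-injected is not given. Alpha, power, sample size and the no-early-stopping decision are unaffected.

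**What to change.** **Main change.** In DSMP 2.3, delete everything from the comma onward, so that the item contains only the rule to stop treatment after a related serious adverse event.

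**Minor alignment.** In the Safety Summary (renal bullet), Statistical Considerations item 2 and Appendix: Pharmacy item 4, replace the wording that implies one dose with a statement along these lines: 80 mg in 40 mL per injection, given again with the same assigned treatment if the subject returns to the operating room for repeat debridement (160 mg in total after one repeat). The sponsor should write any revised renal rationale. In Statistical Considerations only the stated reason changes, not the decision.

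**Cost.** One deleted clause and wording changes in three places. No added patients, visits or tests, and no change to the analysis.
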